#### **Assessment of Causality**

- The investigator is obligated to assess the relationship between study treatment and each occurrence of each AE/SAE.
- A "reasonable possibility" of a relationship conveys that there are facts, evidence, and/or arguments to suggest a causal relationship, rather than a relationship that cannot be ruled out.
- The investigator will use clinical judgment to determine the relationship.
- Alternative causes, such as underlying disease(s), concomitant therapy, and other risk factors, as well as the temporal relationship of the event to study treatment administration will be considered and investigated.
- The investigator will also consult the Investigator's Brochure (IB) and/or Product Information, for marketed products, in his/her assessment.
- For each AE/SAE, the investigator must document in the medical notes that he/she has reviewed the AE/SAE and has provided an assessment of causality.
- There may be situations in which an SAE has occurred, and the investigator has minimal information to include in the initial report to [REDACTED]
- However, **it is very important that the investigator always assess causality for every event before the initial transmission of the SAE data to [REDACTED]**
- The investigator may change his/her opinion of causality in light of follow-up information and send an SAE follow-up report with the updated causality assessment.
- The causality assessment is one of the criteria used when determining regulatory reporting requirements.

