### **3.3. Benefit/risk assessment**

The need for a therapy to significantly reduce the visual morbidity in DR is clear and, if accomplished, would provide great benefit to patients with progressive vision loss. The risk of intravitreal injections is relatively small and well characterized. More detailed information about the known and expected benefits and risks and reasonably expected adverse events of AVD-104 may be found in the Investigator's Brochure.

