## 6. TREATMENTS

### 6.1. Treatments administered

Study Treatment Name:	AVD-104
Dosage formulations:	Group 1: [REDACTED]
	Group 2: [REDACTED]
Unit dose strength(s):	Group 1: [REDACTED]
	Group 2: [REDACTED]
Route of Administration	Intravitreal injection
Dosing instructions:	Group 1: Two injections 56 days apart
	Group 2: Three injections each 28 days apart
Packaging and Labelling	Study treatment will be provided in a sealed container as a frozen suspension.

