## 8. ADVERSE EVENTS

The definitions of an AE and SAE can be found in [Appendix 4](#).

AE will be reported by the participant (or, when appropriate, by a caregiver, surrogate, or the participant's legally authorized representative).

The investigator and any designees are responsible for detecting, documenting, and reporting events that meet the definition of an AE or SAE and remain responsible for following up AEs that are serious, considered related to the study treatment or other aspects of the study, or that caused the participant to discontinue the study treatment or other aspects of the study (see [Section 9](#)).

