### 8.1. Time period and frequency for collecting AE and SAE information

All AEs and SAEs will be collected from the start of treatment until the final follow-up visit at the time points specified in the SoA ([Section 2](#)).

Medical occurrences that begin before the start of study treatment but after obtaining informed consent will be recorded on the Medical History/Current Medical Conditions section of the case report form (CRF).

All SAEs will be recorded and reported to the sponsor or designee within [REDACTED] as indicated in [Appendix 4](#). The investigator will submit any updated SAE data to the sponsor within [REDACTED] of it being available.

Investigators are not obligated to actively seek AE or SAE in former study participants. However, if the investigator learns of any SAE, including a death, at any time after a participant has been discharged from the study, and he/she considers the event to be reasonably related to the study treatment or study participation, the investigator must promptly notify the sponsor.

The method of recording, evaluating, and assessing causality of AE and SAE and the procedures for completing and transmitting SAE reports are provided in [Appendix 4](#)

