5 SAFETY ANALYSES

All safety analyses will be performed using the Safety Population.

The primary safety variable is the incidence and severity of ocular and systemic AEs and SAEs. MedDRA Version 26.1 (September 2023) nomenclature will be used to code adverse events. The number and percent of participants reporting ocular and systemic AEs/SAEs will be tabulated based on the MedDRA System Organ Class and Preferred Term. Summary tables will be generated for all AEs regardless of causality as well as for treatment-related AEs.

The following safety data will be analyzed and presented in tabular format:

- Overview of Treatment Emergent Adverse Events
- Summary of Adverse Events by System Organ Class and Preferred Term
- 

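### The treatment-related AE table cannot separate AVD-104 effects from intravitreal injection effects, because no procedure attribution is recorded or tabulated in the readable plan

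*Protocol*

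**What the plan says.** Protocol Appendix 4, under Assessment of Causality, sets the rule: "The investigator is obligated to assess the relationship between study treatment and each occurrence of each AE/SAE". Protocol section 6.1 names the study treatment as AVD-104. It describes a supplied product ("Study treatment will be provided in a sealed container as a frozen suspension") and lists intravitreal injection as the route. The alternative causes to be weighed in Appendix 4 are given as "Alternative causes, such as underlying disease(s), concomitant therapy, and other risk factors"; the injection is not named among them.

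The protocol recognises causes other than the drug. Section 3.3 states: "The risk of intravitreal injections is relatively small and well characterized". Section 8 sets the follow-up duty partly by whether an event is "considered related to the study treatment or other aspects of the study". Section 8.1 uses "reasonably related to the study treatment or study participation" for SAEs learned of after discharge.

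SAP section 5 defines the outcome: "The primary safety variable is the incidence and severity of ocular and systemic AEs and SAEs". It then plans the causality output: "Summary tables will be generated for all AEs regardless of causality as well as for treatment-related AEs". SAP section 5.1 refers to protocol Appendix 4 for how causality is assessed and adds no category of its own.

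**The concern.** Many ocular events after an intravitreal injection, such as a conjunctival haemorrhage at the needle site, can come from the needle or the injected volume rather than the product. With a single related/unrelated answer, one investigator may count such an event as related because the injection delivers the treatment. Another may count it as unrelated because AVD-104 did not cause it. The resulting table mixes the two conventions, and a reader cannot undo the mixture from the table.

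The design offers no independent way to separate them. Both groups receive AVD-104 by injection, and no sham or vehicle group is described. Dose is also tied to injection count, so a difference between arms in treatment-related events could reflect dose, number of injections or attribution habit. Safety and tolerability is the only primary objective, and this table is the only readable planned summary that attributes events to treatment.

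**Working it through.** **Text check.** The readable passages on causality and AE tabulation, set side by side:

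| Place | What it governs | Separate injection attribution recorded or tabulated? |
|---|---|---|
| Protocol 3.3 | Benefit/risk background | No |
| Protocol 6.1 | Identity and route of study treatment | No |
| Protocol 8 | Which AEs must be followed up | No; wider wording, follow-up only |
| Protocol 8.1 | SAEs learned of after discharge | No; wider wording, notification only |
| Appendix 4, Assessment of Causality | The judgement made for each AE/SAE | No; study treatment only |
| SAP 5 | AE tables | No; all-causality and treatment-related |
| SAP 5.1 | Source of causality rules | No; refers to Appendix 4 |

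The protocol therefore mentions causes beyond the drug in three places (3.3, 8 and 8.1), but none of these reaches the causality record in Appendix 4 or the tables in the SAP.

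**Scale.** The plan states no figure on this point, so there is none to reproduce. Inputs from the Schedule of Activities and the synopsis: 15 participants with 3 injections (low dose) and 15 with 2 injections (high dose).

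- Planned injections: 15 × 3 = 45 and 15 × 2 = 30, in total 75. The ratio is 45/30 = 1.5.
- Assumption, not in the documents: each injection carries an independent risk p of a purely procedural AE.
- Probability that a participant has at least one: 1 − (1 − p)^k, with k = 3 or 2.
- At p = 0.05: 1 − 0.95³ = 14.3% and 1 − 0.95² = 9.8%.
- At p = 0.15: 1 − 0.85³ = 38.6% and 1 − 0.85² = 27.8%.
- Expected participants of 30: 15 × (low-dose share + high-dose share).

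| Assumed p | Low dose | High dose | Difference (percentage points) | Expected participants of 30 |
|---|---|---|---|---|
| 1% | 3.0% | 2.0% | 1.0 | 0.7 |
| 5% | 14.3% | 9.8% | 4.5 | 3.6 |
| 10% | 27.1% | 19.0% | 8.1 | 6.9 |
| 15% | 38.6% | 27.8% | 10.8 | 10.0 |
| 20% | 48.8% | 36.0% | 12.8 | 12.7 |

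At a given p, the share columns are upper limits on the participants whose classification could depend on the convention. They are reached only if every procedural event is called related under one convention and unrelated under the other. The difference column is what would arise between arms with no drug effect, if all procedural events were called related.

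**The case against.** Four stronger readings are tempting, and the documents do not support them.

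- **The primary safety result is compromised.** It is not. The primary safety variable carries no causality condition, and tables by System Organ Class and Preferred Term are planned regardless of causality. Attribution cannot change them. SAP sections 2.6 and 3.1 also put all data in listings, so with at most 30 participants events can be read one by one. No readable test or decision rule uses the treatment-related count.
- **The text endorses both answers equally.** It leans towards the product. Section 6.1 describes a supplied suspension, Appendix 4 distinguishes the treatment from its administration, and section 8 distinguishes it from other aspects of the study. Appendix 4 also asks for positive grounds for a relationship, not merely that one cannot be excluded. Some ambiguity remains, because the injection is not named as an alternative cause and timing cannot separate a drug and a needle that arrive together.
- **The judgement leaves no trace.** Appendix 4 requires a causality assessment documented in the medical notes. What is missing is a structured procedure answer that can be tabulated.
- **The related rate will swing from zero to 39%.** That is an extreme under an assumed rate, not an expected effect. An abnormal finding such as a brief pressure rise counts as an AE only if judged clinically significant, so some procedural effects may never enter the tables.

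The absence is also only partly visible. The AE CRF page was not supplied. The visual-safety guidance (section 8.5.2) and the SAE reporting text in Appendix 4 are redacted, and the table list in SAP section 5 ends in an empty bullet. A procedure field or table may exist there. What stands is that the causality rule and the sentence on causality tables are themselves readable and contain none.

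**Conclusion.** The point holds for the supplementary treatment-related table only. In the readable plan each AE is attributed to study treatment or not, so that table cannot separate AVD-104 effects from injection effects. Part of any excess in the low-dose arm could come from the third injection alone.

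The share of participants open to reclassification is at most 14% to 39% (low dose) and 10% to 28% (high dose), about 4 to 10 of 30. This assumes a 5% to 15% procedural risk per injection, independence between injections, and 15 participants per arm receiving all planned injections. At a 1% risk it is less than one participant. The conclusion about the table does not depend on these rates; only its practical size does. This is a worthwhile, inexpensive improvement and not a flaw in the primary analysis.

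**What to change.** In protocol Appendix 4, and on the AE CRF page if it is not already there, record two answers for each AE: related to AVD-104 (yes/no), and related to the injection or another study procedure (yes/no). In SAP section 5, keep the combined treatment-related table. Add an AVD-104-related table and a procedure-related table, each by System Organ Class, Preferred Term and arm, and count an event in both when both answers are yes.

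The cost is a sentence in Appendix 4, at most one CRF field and two further tables. If the CRF already holds the field, only Appendix 4 and the SAP need aligning. The answers should be captured when each event is assessed, because later reconstruction would be retrospective.

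There are two limits. Some events cannot be separated and will be ticked for both. The extra field also records investigator judgement, and protocol section 6.3 names only the reading center and the vision examiner as masked. It does not supply a procedural background rate, which this design without a sham or vehicle group cannot provide.

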#### **Follow-up of AE and SAE**

- The investigator is obligated to perform or arrange for the conduct of supplemental measurements and/or evaluations as medically indicated or as requested by the Medical Monitor or Sponsor to elucidate the nature and/or causality of the AE or SAE as fully as possible. This may include additional laboratory tests or investigations, histopathological examinations, or consultation with other health care professionals.
- If a participant dies during participation in the study or during a recognized follow-up period, the investigator will provide [REDACTED] with a copy of any post-mortem findings including histopathology.
- New or updated information will be recorded in the originally completed CRF.
- The investigator will submit any updated SAE data to the sponsor within [REDACTED] of receipt of the information.

**Reporting of SAE** [REDACTED]

[REDACTED]

[REDACTED]

[REDACTED]

[REDACTED]

[REDACTED]

[REDACTED]

[REDACTED]

## Appendix 5. Contraceptive guidance and collection of pregnancy information

### Definitions

#### Woman of Childbearing Potential (WOCBP)

A woman is considered fertile following menarche and until becoming postmenopausal unless permanently sterile. Permanent sterilization methods include hysterectomy, bilateral salpingectomy, and bilateral oophorectomy.

#### Women in the following categories are not considered WOCBP

1. Premenopausal female with 1 of the following:
  - Documented hysterectomy
  - Documented bilateral salpingectomy
  - Documented bilateral oophorectomy

Note: Documentation can come from the site personnel's: review of participant's medical records, medical examination, or medical history interview.

2. Premenarchal
3. Postmenopausal female
  - A postmenopausal state is defined as no menses for 12 months without an alternative medical cause. A high follicle-stimulating hormone (FSH) level in the postmenopausal range may be used to confirm a postmenopausal state in women not using hormonal contraception or hormonal replacement therapy (HRT). However, in the absence of 12 months of amenorrhea, a single FSH measurement is insufficient.
  - Females on HRT and whose menopausal status is in doubt will be required to use one of the non-hormonals highly effective contraception methods if they wish to continue their HRT during the study. Otherwise, they must discontinue HRT to allow confirmation of postmenopausal status before study enrollment.

### Contraception guidance

#### Male participants

- Male participants with female partners of childbearing potential are eligible to participate if they agree to the following during the protocol-defined time frame:
  - Are abstinent from penile-vaginal intercourse as their usual and preferred lifestyle (abstinent on a long-term and persistent basis) and agree to remain abstinent for duration of study and for 3 months after study completion or from last dose
  - Female partner is using a highly effective contraceptive method
- Agree to use a male condom plus an additional method with a failure rate of <1% per year as described in the table below when having penile-vaginal intercourse with a woman of childbearing potential.
- Men with a pregnant or breastfeeding partner must agree to remain abstinent from penile-vaginal intercourse or use a male condom during each episode of penile penetration during the protocol-defined time frame.
- Refrain from donating sperm for duration of study and for 3 months from last dose of study drug.

Highly Effective Contraceptive Methods That Are User Dependent Failure rate of <1% per year when used consistently and correctly.	
Combined (estrogen- and progestogen-containing) hormonal contraception associated with inhibition of ovulation b 
 
• Oral
 
• Intravaginal
 
• Transdermal
 
	
Progestogen-only hormonal contraception associated with inhibition of ovulation 
 
• Oral
 
• Injectable
 
	
Highly Effective Methods That Are User Independent 
 
• Implantable progestogen-only hormonal contraception associated with inhibition of ovulationb
 
• Intrauterine device (IUD)
 
• Intrauterine hormone-releasing system (IUS)
 
• Bilateral tubal occlusion
 
	
Vasectomized partner (A vasectomized partner is a highly effective contraception method provided that the partner is the sole male sexual partner of the WOCBP and the absence of sperm has been confirmed. If not, an additional highly effective method of contraception should be used.)	
Sexual abstinence (Sexual abstinence is considered a highly effective method only if defined as refraining from heterosexual intercourse during the entire period of risk associated with the study drug. The reliability of sexual abstinence needs to be evaluated in relation to the duration of the study and the preferred and usual lifestyle of the participant.)	
NOTES: 
 
a) Typical use failure rates may differ from those when used consistently and correctly. Use should be consistent with local regulations regarding the use of contraceptive methods for participants participating in clinical studies.
 
	

## Female participants

Female participants of reproductive potential are eligible to participate if they agree to use a highly effective method of contraception consistently and correctly as described in the table above.

## Pregnancy testing

- WOCBP should only be included after a confirmed menstrual period and a negative highly sensitive urine (dipstick or microscopy) pregnancy test
- Pregnancy testing urine testing will be performed at screening, M12, and M24. If the urine test is positive, it should be confirmed by serum testing.
- Pregnancy testing will be performed whenever a menstrual cycle is missed or when pregnancy is otherwise suspected

## Collection of pregnancy information

## Male participants with partners of reproductive potential who become pregnant

- Investigator will attempt to collect pregnancy information on any female partner of a male study participant who becomes pregnant while participating in this study. This applies only to participants who receive study treatment.
- After obtaining the necessary signed informed consent from the pregnant female partner directly, the investigator will record pregnancy information on the appropriate form and submit it to the sponsor within [REDACTED] of learning of the partner's pregnancy.
- Partner will also be followed to determine the outcome of the pregnancy. Information on the status of the mother and child will be forwarded to the sponsor.
- Generally, follow-up will be no longer than [REDACTED] following the estimated delivery date. Any termination of the pregnancy will be reported regardless of fetal status (presence or absence of anomalies) or indication for procedure.

#### **Female participants who become pregnant**

- Investigator will collect pregnancy information on any female participant, who becomes pregnant while participating in this study.
- Information will be recorded on the appropriate form and submitted to the sponsor within [REDACTED] of learning of a participant's pregnancy.
- Participant will be followed to determine the outcome of the pregnancy. The investigator will collect follow-up information on participant and neonate, which will be forwarded to the sponsor. Generally, follow-up will not be required for longer than 6 to 8 weeks beyond the estimated delivery date.
- Any termination of pregnancy will be reported, regardless of fetal status (presence or absence of anomalies) or indication for procedure.
- While pregnancy itself is not considered to be an AE or SAE, any pregnancy complication or elective termination of a pregnancy will be reported as an AE or SAE.
- A spontaneous abortion is always considered to be an SAE and will be reported as such.
- Any SAE occurring as a result of a post-study pregnancy, which is considered reasonably related to the study treatment by the investigator, will be reported to the sponsor as described in [Appendix 4](#) While the investigator is not obligated to actively seek this information in former study participants, he or she may learn of an SAE through spontaneous reporting.

Any female participant who becomes pregnant while participating:

- Will discontinue study treatment but not be withdrawn from the study

1 INTRODUCTION

Protocol Number: AVD-104-C301

Protocol Title: A Phase 2 Study to Evaluate the Safety, and Treatment Effect of Intravitreal AVD-104 in Participants with Diabetic Macular Edema (DME).

Rationale: To determine the safety and preliminary efficacy of intravitreal injections of AVD-104, a novel glyco-mimetic nanoparticle, in reducing macular edema associated with diabetic retinopathy.

1.1 Trial Objectives

Primary Objective:

- Evaluate the safety and tolerability of AVD-104 in participants with DME.

Secondary Objectives:

- Evaluate the treatment effect of AVD-104 at multiple doses on central subfield thickness (CST) as measured by Spectral-domain optical coherence tomography (SD-OCT).
- Evaluate the treatment effect of AVD-104 at multiple doses on Best-corrected visual acuity (BCVA) using ETDRS (Early-Treatment Diabetic Retinopathy Study) visual acuity charts.

Exploratory Objective:

- [REDACTED]

2 STUDY DESIGN

2.1 Trial rationale and Description of the Design

The trial will be a multi-center, randomized evaluation of the effect of AV-104 in participants with diabetic macular edema. Participants will undergo baseline examinations to include BCVA, slit lamp and indirect ophthalmoscopy, both spectral domain OCT and OCT angiography, and ultrawide-field fluorescein angiography analysis.

For all potential participants, eligibility based on severity of diabetic retinopathy must be confirmed by the central reading center prior to participant enrollment. In addition, all screening laboratory tests must be performed, and the results must be evaluated and determined to be acceptable by the investigator prior to participant enrollment into the study.

Participants will then be randomized to one of two different groups:

- Group 1: Two (2) injections of high-dose AVD-104 [REDACTED]
- Group 2: Three (3) injections of low-dose AVD-104 [REDACTED].

Participants will be carefully monitored over the next [REDACTED] days with repeat evaluations to ascertain any effect from AVD-104. Specific rescue criteria will allow the participants to be treated with the current standard-of-care agents should there be any significant decline in their vision.

The end of the study is defined as the date of the last visit of the last participant in the study.

The trial is designed to provide initial efficacy data for AVD-104 in participants with DR. The parameters evaluated will include change in vision, change in CST on OCT, [REDACTED]

